KIRIKKALE UNIVERSITY

FACULTY OF MEDICINE

DEPARTMENT OF CARDIOLOGY

STUDY DOCUMENTS OF

“Association Between SYNTAX Score and Leukoglycemic Index

In Patients With Acute Coronary Syndrome”

PROTOCOL ID: 2024.05.19

NCT NUMBER: NCT07276256

DATE OF ISSUE: 15.12.2025

RESPONSIBLE RESEARCHER: [name],

MD

Study Design and Methods

Our study was designed as a single-center, retrospective, cross-sectional, observational study. It was conducted after approval by the Ethics Committee of the Faculty of Medicine, Kırıkkale University. Patients who presented to the emergency department or cardiology outpatient clinic between 2015 and 2023 with suspected acute coronary syndrome (ACS) and underwent coronary angiography were retrospectively evaluated.

In this study, the SYNTAX scores of patients diagnosed with ACS and who underwent coronary angiography, followed by a decision for Percutaneous Coronary Intervention (PCI) or Coronary Artery Bypass Grafting (CABG), were calculated and their relationship with the Leucoglycemic Index (LGI) was investigated.

Between 2015 and 2023, a total of 1209 patients presenting to the cardiology outpatient clinic or emergency department of Kırıkkale University Faculty of Medicine with ACS were retrospectively screened. After applying exclusion criteria, 552 patients were included in the study.

Coronary angiography images were retrieved from the hospital's Picture Archiving and Communication System (PACS). Using quantitative coronary angiography (QCA), lesions were defined as significant obstructive coronary artery disease (CAD) if there was >50% stenosis in the left main coronary artery (LMCA) or >70% stenosis in coronary arteries with a diameter >1.5 mm. SYNTAX scores were calculated using the official SYNTAX Score Calculator website.

Standard laboratory tests performed at admission were retrospectively obtained from the hospital information system. Complete blood count and biochemical data were recorded. The LGI value was calculated as the product of blood glucose (mg/dL) and leukocyte count ($10^9/L$), divided by 1000.

Formula:

$$LGI = [\text{Glucose (mg/dL)} * \text{Leukocyte count (10}^9\text{/L)}] / 1000$$

Inclusion Criteria

- Adults aged ≥ 18 years
- Patients undergoing coronary angiography due to acute coronary syndrome
- Non-obese patients

Exclusion Criteria

- Patients <18 years of age
- Patients with diabetes mellitus (diagnosed by ongoing oral or insulin therapy and/or fasting glucose ≥ 126 mg/dL with HbA1c $\geq 6.5\%$)
- Patients with atrial fibrillation, pacemaker history, asthma, pulmonary hypertension, pregnancy, anemia, malignancy, rheumatoid arthritis, peripheral artery disease

- Obese patients (BMI >30 kg/m²)
- Patients with unavailable medical records

Study Variables

- **Independent variables:** Age, sex, comorbidities, laboratory results (white blood cell count, hemoglobin, platelet count, glucose), SYNTAX score
- **Dependent variables:** Admission hemogram and glucose values

Statistical Analysis

Data analysis was performed using SPSS for Windows, version 25.

- Categorical variables were expressed as frequencies and percentages.
- Continuous variables were expressed as mean \pm standard deviation or median (minimum–maximum), depending on distribution.
- Relationships between categorical variables were assessed using the Chi-square test.
- For continuous variables, normality was tested with the Shapiro–Wilk test and homogeneity of variance with the Levene test.
- Normally distributed data were compared using the independent samples Student's t-test; non-normally distributed data were analyzed with the Mann–Whitney U test.
- The relationship between LGI and SYNTAX score was evaluated using Pearson correlation analysis.
- Logistic regression analysis was used to identify predictors of moderate-to-high SYNTAX scores. Odds ratios (OR) and confidence intervals (CI) were calculated, with non-critical CAD as the reference.
 - In the unadjusted model, only LGI was used to predict CAD severity.
 - In the adjusted model, age, HbA1c, creatinine, and hypertension were included in multivariate logistic regression.
- Linear regression analysis was also performed to assess the relationship between LGI and CAD severity.
- Results were interpreted according to p-values, with $p < 0.05$ considered statistically significant.

Ethics Approval

The study was approved by the Non-Interventional Research Ethics Committee of Kırıkkale University Faculty of Medicine on May 22, 2024, with decision number 2024.05.19.

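### Acute infection, systemic steroids, shock and cardiac arrest at admission are neither excluded, recorded nor adjusted for, so extreme LGI values may influence the LGI–SYNTAX result; counts and a labelled sensitivity analysis are needed

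*Combined protocol and SAP*

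**What the plan says.** Under Study Design and Methods, the exposure comes from a single time point: "Standard laboratory tests performed at admission were retrospectively obtained from the hospital information system". It is a product of two of those values: "The LGI value was calculated as the product of blood glucose (mg/dL) and leukocyte count", divided by 1000. The source population is broad: "Between 2015 and 2023, a total of 1209 patients presenting to the cardiology outpatient clinic or emergency department". The clinical entry condition under Inclusion Criteria is "Patients undergoing coronary angiography due to acute coronary syndrome", with no restriction on haemodynamic state or infection.

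The Exclusion Criteria list age under 18, diabetes, nine named conditions ("Patients with atrial fibrillation, pacemaker history, asthma, pulmonary hypertension, pregnancy, anemia, malignancy, rheumatoid arthritis, peripheral artery disease"), BMI above 30 and "Patients with unavailable medical records". Diabetes is the only glucose-related exclusion: "Patients with diabetes mellitus (diagnosed by ongoing oral or insulin therapy and/or fasting glucose ≥ 126 mg/dL with HbA1c" at or above 6.5%.

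Under Statistical Analysis, LGI and SYNTAX score are related by Pearson correlation, logistic regression and linear regression. For the logistic model, "In the adjusted model, age, HbA1c, creatinine, and hypertension were included in multivariate logistic regression". No transformation of LGI, rank correlation or sensitivity analysis is described for the LGI–SYNTAX relation.

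**The concern.** One admission glucose and one admission leukocyte count reflect whatever is acting on the patient that day. Active infection, systemic corticosteroids, shock and resuscitated arrest can raise both values, and multiplication compounds the rise. These patients would lie in the far right tail of LGI. Pearson correlation, and a regression that is linear in LGI, give that tail disproportionate weight.

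The existing safeguards do not cover this. Acute or steroid-related hyperglycaemia with HbA1c below 6.5% and no diabetes treatment passes the diabetes exclusion. HbA1c in the model reflects longer-term glycaemia. No covariate measures acute leukocytosis, infection or steroid exposure, and creatinine is at best a weak proxy for shock.

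At stake is how the main result is read. If affected patients have SYNTAX scores similar to or lower than the rest, a real association is diluted. If they have higher scores, a handful could produce much of the observed correlation. The plan provides no way to tell which applies.

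**Working it through.** **What the documents allow.** They give no power, effect-size or LGI distribution figure, so there is nothing to reproduce. The usable inputs are n = 552 (from 1209 screened) and the 0.05 threshold, taken here as two-sided because sidedness is not stated. Everything else below is an assumption.

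**Step 1: coverage.** Neither the exclusion list, the Study Variables section (age, sex, unspecified comorbidities, laboratory results, SYNTAX score) nor the four adjustment covariates names any of the four acute states.

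**Step 2: what n = 552 can detect.** By Fisher's z, the smallest significant |r| is tanh(1.96/√549) = 0.083. For 80% power, r = tanh((1.96 + 0.84)/√549) = 0.119.

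**Step 3: mixture formula.** Let a share p of patients have LGI shifted by dL SD and SYNTAX by dS SD, let the within-group correlation be r0, and let q = p(1 − p). Then

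r_obs = (r0 + q·dL·dS) / √[(1 + q·dL²)(1 + q·dS²)].

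- Unrelated to SYNTAX (r0 = 0.12, p = 5%, q = 0.0475, dS = 0): dL = 2 gives 0.12/√1.19 = 0.110; dL = 3 gives 0.12/√1.4275 = 0.100. Power falls from about 80% to 74% and 66%. With r0 = 0.20 it stays at 94% or more in every case tried, including p = 10%.
- No true association, affected patients with higher SYNTAX (r0 = 0, p = 5%, dL = 2, dS = 1): 0.095/√(1.19 × 1.0475) = 0.085, significant in about 52% of studies.
- Rare and mild (r0 = 0, p = 2%, dL = 1, dS = 0.5): r = 0.010, significant in about 6%, close to the nominal 5%.

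**Step 4: simulation on the LGI scale.** Assumed log-normal glucose (median 115 mg/dL) and leukocytes (median 9), with log-SDs of 0.2 and 0.3 unless stated otherwise.

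- True r about 0.145, nobody affected: detected in about 93% of studies.
- 5% infected (leukocytes +6, glucose +20), SYNTAX unaffected: r about 0.13, detection about 86%.
- Same, but SYNTAX 0.5 SD lower: r about 0.08, detection about 43%. With log-SDs of 0.3 and 0.4, about 61%. At 1% infected, about 87%.
- No true association, 3% in shock or arrest (leukocytes +6, glucose +100, SYNTAX 1 SD higher): r about 0.11, significant in about 73%. With log-SDs of 0.3 and 0.4, 52–54%. At 1%, between 12% and 22% depending on spread.
- Milder shift at 3% (+5, +60, 0.5 SD): r about 0.04, significant in about 18%.
- In the 3% shock scenario, a rank correlation cuts the significant results to about 20%. Leaving out the flagged patients returns r to about 0 and significance to about 5%.

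**The case against.** There are five serious counter-arguments.

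1. *Nothing shows that affected patients are in the cohort.* This stands. A reader might infer that the reported correlation is biased. The documents support only that such patients are eligible as the criteria are written.

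2. *Strong masking needs infected patients with low SYNTAX scores.* A reader might picture a patient with pneumonia, a troponin rise and near-normal coronaries. Study Design and Methods describes scoring patients diagnosed with ACS whose angiography led to a PCI or CABG decision, which speaks against such a patient being scored. Statistical Analysis, however, uses a non-critical CAD reference group, so low-burden patients appear to be analysed. The case can be neither assumed nor ruled out. Without it, the loss is slight.

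3. *Shock and arrest may belong to ACS.* This also stands. If patients in shock have both higher LGI and more complex disease, that is part of the association in the population the study names. Calling it spurious would redefine the target as ACS without shock, which the protocol does not claim. Infection and steroid use differ in being extraneous to coronary anatomy.

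4. *Much of the effect is leverage, which ranks or logs would reduce.* Partly right. A rank analysis helps, but in the 3% shock scenario about 20% of studies remain significant, so it complements flagging without replacing it.

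5. *The study has been run, and new exclusions would be post hoc.* Correct, and a reason not to change eligibility or move the conclusion to a reduced cohort. It does not count against a sensitivity analysis labelled as such.

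A reader might also see the exclusion list as a screen for chronic inflammation that forgot acute inflammation. The list does not support this: atrial fibrillation, pacemaker, pregnancy and anemia are on it too. The point rests on how LGI is built.

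**Conclusion.** The omission is real: four acute states that can produce extreme LGI values are absent from the exclusions, recorded variables, covariates and sensitivity analyses. The resulting bias is possible, not demonstrated. With assumed frequencies of 1–5%, it ranges from negligible to enough to halve detection of a modest association or to produce a significant one in most studies. Those extremes require affected patients to differ in SYNTAX score and LGI to be fairly tightly distributed in everyone else. Neither is known from the documents. Infection or steroid use unrelated to SYNTAX has a small attenuating effect, and an association near r = 0.20 would survive it. For shock and arrest, the documents do not establish whether their influence is contamination or part of the association of interest. That supports showing the result with and without them. It does not support a claim that the main analysis is invalid.

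**What to change.** From the records already screened, flag two groups:

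- (a) active infection at admission, including a positive SARS-CoV-2 test, or systemic corticosteroid use at admission;
- (b) cardiogenic shock or resuscitated cardiac arrest before the blood sample.

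Report the count in each group. Keep the 552-patient analysis as the main one. Add sensitivity analyses, labelled as added after the fact, that repeat the LGI–SYNTAX correlation and the adjusted logistic model first without group (a), then without groups (a) and (b). Give the correlation also on ranks or with log-LGI, both in the full cohort and in the reduced sets. If results differ, report both and limit the conclusion accordingly; do not switch to the reduced cohort.

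The cost is a second pass through the records and some extra analysis. If the counts are close to zero, one sentence settles the matter.

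### Pearson is the only correlation named for LGI and SYNTAX, and the plan's normality-based switch is not extended to it, so a few extreme LGI values could move the estimate

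*Combined protocol and SAP*

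**What the plan says.** All references are to the combined protocol and SAP.

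- **Correlation (Statistical Analysis).** "The relationship between LGI and SYNTAX score was evaluated using Pearson correlation analysis". No rank-based alternative, transformation, outlier rule or influence check is given.
- **Distribution checks (same section).** For continuous variables, "normality was tested with the Shapiro–Wilk test". Summaries are a mean with SD or a "median (minimum–maximum), depending on distribution". For group comparisons, "non-normally distributed data were analyzed with the Mann–Whitney U test".
- **Definition of LGI (Study Design and Methods).** "The LGI value was calculated as the product of blood glucose (mg/dL) and leukocyte count", scaled by 1000. Both components are admission values.
- **Sample.** "After applying exclusion criteria, 552 patients were included in the study". No sample-size or power calculation is given.
- **Other LGI analyses (Statistical Analysis).** There are unadjusted and adjusted logistic models for moderate-to-high SYNTAX, and a linear regression. No analysis is labelled primary.

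**The concern.** The plan lets the data's distribution decide the method for summaries and two-group tests, but not for the association that the title asks about. That association is where the distribution could matter most.

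Multiplying two positive quantities compounds their skew and their extremes. The exclusion list trims the upper tail of LGI without removing it. The laboratory route to the diabetes exclusion needs both a raised fasting glucose and HbA1c of at least 6.5%, so a patient with high admission glucose and lower HbA1c stays in. Acute infection is not on the list, so a leukocyte count raised for an unrelated reason can stay in too.

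Pearson's r weights each patient by squared distance from the mean. A handful of very high LGI values can therefore carry much of the estimate. At stake are the size of the reported correlation and whether it reaches significance.

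**Working it through.** The documents give no correlation, power or distribution figure, so there is nothing of the plan's to reproduce.

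**Inputs from the documents:** n = 552; significance level 0.05 (sidedness not stated, two-sided assumed); LGI = glucose × leukocytes / 1000.

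**Assumed inputs:** log-normal LGI; SYNTAX with a share of zeros and a gamma tail; latent correlation of 0, 0.15 or 0.30; number and size of extreme LGI values as stated in each step.

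**1. What 552 patients can detect.** With Fisher's z, SE = 1/√(552 − 3) = 0.0427. The detectable r is tanh[(1.960 + 0.842)/√549] = 0.119 at 80% power and tanh[(1.960 + 1.282)/√549] = 0.138 at 90%. Power is 94% for r = 0.15, 81% for 0.12 and 65% for 0.10. A weak association is therefore sensitive to modest attenuation.

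**2. Skew alone.** Take coefficients of variation (CVs) of 0.20–0.50 for glucose and 0.30–0.50 for leukocytes, with 0–20% zeros in SYNTAX. At latent 0.30, mean Pearson is 0.268–0.282 and mean Spearman 0.283–0.287. At latent 0.15, over a range of skew, Pearson is about 0.004–0.010 lower (power 84–92% against 89–93%). At latent 0, both reject in about 5% of runs. Shapiro–Wilk rejected normality of LGI in every simulated sample checked. This follows from the log-normal assumption, but it shows that the plan's own test would then point to a rank method.

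**3. Five extreme values (5/552 = 0.9%).** Simulation with 1,500 runs per row, glucose CV 0.25, leukocyte CV 0.30 and 20% zeros:

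| Latent r | Five LGI values set to | Placed in | Pearson | Spearman | Significant, Pearson / Spearman |
|---|---|---|---|---|---|
| 0.15 | none | – | 0.139 | 0.141 | 90% / 91% |
| 0.15 | 3 × mean | random | 0.125 | 0.140 | 83% / 92% |
| 0.15 | 5 × mean | random | 0.099 | 0.138 | 63% / 91% |
| 0.15 | 5 × mean | low SYNTAX | 0.029 | 0.117 | 5% / 78% |
| 0.15 | 5 × mean | high SYNTAX | 0.234 | 0.161 | 100% / 98% |
| 0.30 | none | – | 0.281 | 0.284 | 100% / 100% |
| 0.30 | 5 × mean | random | 0.203 | 0.280 | 100% / 100% |
| 0.30 | 5 × mean | low SYNTAX | 0.128 | 0.253 | 92% / 100% |
| 0.30 | 5 × mean | high SYNTAX | 0.334 | 0.299 | 100% / 100% |

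The random rows can be checked by hand. The squared CV of LGI is (1 + 0.25²)(1 + 0.30²) − 1 = 0.158. In units of the squared mean, the LGI sum of squares is therefore about 552 × 0.158 = 87. Five values at 5 × the mean add about 5 × (5 − 1)² = 80. If they are unrelated to SYNTAX, r shrinks by about √(87/167) = 0.72. That gives 0.139 × 0.72 = 0.100 and 0.281 × 0.72 = 0.202, against 0.099 and 0.203 simulated.

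**4. Multiplicative extremes unrelated to SYNTAX.** Latent r = 0.15, SD of log LGI 0.4–0.6, 0–30% zeros:

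- 6 patients (1.1%) at 2 × their value: Pearson 0.124–0.133.
- 6 patients at 3 ×: Pearson 0.120–0.125, power 79–83%.
- 11 patients (2.0%) at 4 ×: Pearson 0.096–0.111, power 60–72%.
- Over 6–11 patients at 3–4 ×, Spearman stays at 0.134–0.141, power 88–91%.

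**5. Whether the other analyses protect the result.** If the linear regression has a single predictor, its slope test is algebraically the Pearson test, so it is no independent check. No transformation of LGI is stated for the logistic models, so extreme values keep their leverage there.

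**The case against.** The strongest reply is that nothing in the documents shows skew, outliers or a distorted result. That stands. A reader might infer that the reported correlation is wrong, but without a distribution or a result only *can distort* is supportable. The 60% power figure in particular needs about 2% of patients at four times their LGI, a prevalence for which the documents give no evidence.

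Other parts of the defence also stand:

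- Skew by itself is a minor issue at this sample size, and false-positive rates stay near 5%.
- With extremes unrelated to SYNTAX, the average effect is attenuation. Mean Pearson rose only when the extremes were placed in high-SYNTAX patients.
- A reader might take the correlation to be the main estimate. The title and aim make it a candidate, but no analysis is named primary and the adjusted logistic model is equally plausible.
- A cluster of zero SYNTAX scores is uncertain. The methods describe scoring in patients with a revascularisation decision, while the logistic model uses non-critical disease as its reference category. The documents do not say whether the latter patients enter the correlation.
- The text is in the past tense and lists the normality test before the correlation, so Pearson may have been chosen after that check. The documents do not say either way.
- Logistic regression needs no normal predictor, and log(LGI) changes what the odds ratio means. A compulsory log transformation in every model does not follow from this point.

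What the defence does not remove is the gap itself: one distribution rule for summaries and group tests, and none stated for the title association.

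**Conclusion.** The inconsistency is certain from the text; its effect on the result is conditional. With 552 patients, a latent correlation of 0.15 and an assumed 1–2% of patients with LGI three to four times higher for unrelated reasons, Pearson can fall to about 0.10–0.12 with power about 60–80%, against about 0.13–0.14 and 88–91% for Spearman. With five values at five times the mean placed deliberately in low- or high-SYNTAX patients, Pearson moved by −0.11 to +0.10 at latent 0.15 and by −0.15 to +0.05 at latent 0.30; Spearman moved by about 0.03 or less. The direction therefore cannot be stated in advance, and only the study data can settle the size. The point merits a change because the remedy is cheap, not because an error has been shown.

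**What to change.** - Report Spearman's rho with a 95% CI for LGI against SYNTAX. Keep the stated Pearson result beside it, and add Pearson on log(LGI) as a sensitivity analysis.
- Label the rank analysis as added after data collection, since the document describes analyses already done.
- Show a scatter plot of LGI against SYNTAX, and state whether patients with non-critical disease are in it.
- Check influence in the linear and logistic models, and use log(LGI) there only as a sensitivity analysis.
- If Pearson was chosen after a normality check, say so and give the result.

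The cost is one extra analysis in the same software on data already held, a few lines of text, and slightly lower efficiency for the rank method if the data are in fact bivariate normal.

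### The adjusted logistic model omits sex, a listed variable, and no analysis accounts for ACS type or presentation route, so residual confounding of the LGI odds ratio cannot be excluded.

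*Combined protocol and SAP*

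**What the plan says.** The Statistical Analysis section describes two logistic models. The outcome is set by "Logistic regression analysis was used to identify predictors of moderate-to-high SYNTAX scores", with non-critical coronary disease as reference. For the first model, "In the unadjusted model, only LGI was used to predict CAD severity". For the second, "In the adjusted model, age, HbA1c, creatinine, and hypertension were included in multivariate logistic regression". I read the second as LGI plus those four terms, although the sentence does not name LGI.

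Study Variables gives the independent variables as "Age, sex, comorbidities, laboratory results (white blood cell count, hemoglobin, platelet count, glucose), SYNTAX score". Sex is on that list but in neither model. HbA1c and creatinine are in the model but not named on the list. No reason is given for the choice of covariates.

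The cohort is broad. Inclusion requires only "Patients undergoing coronary angiography due to acute coronary syndrome", and patients "presented to the emergency department or cardiology outpatient clinic between 2015 and 2023". ACS type is not defined or listed anywhere. Route is described but is never a variable, a stratum or a sensitivity analysis. On the timing of the exposure: "Standard laboratory tests performed at admission were retrospectively obtained from the hospital information system".

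**The concern.** LGI is the product of glucose and leukocyte count, taken while an acute event is under way. If more acute presentations have higher LGI and also more obstructive anatomy, LGI and SYNTAX will be associated even if LGI carries no information on disease severity within a given type of presentation.

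None of the four covariates measures acuteness. HbA1c reflects longer-term glycaemia, and its range is already narrowed by the diabetes exclusion. The other analyses do not fill the gap: the Pearson correlation has no covariates, and the linear regression names none.

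The plan judges its results by p < 0.05. What is at stake is whether a significant adjusted odds ratio can be read as an association of LGI with coronary severity beyond the mix of presentations.

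**Working it through.** **Is there a figure to reproduce?** No. The plan gives no power calculation, effect size or event count. The omission is established by setting the model beside the variable list. The rest is an illustration of how large the resulting bias could be.

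**Inputs from the documents:** N = 552; significance level 0.05 (two-sided assumed); binary outcome of moderate-to-high SYNTAX.

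**Assumed inputs:** one omitted binary factor U with prevalence p. It shifts LGI by d1 SD and the underlying SYNTAX scale by d2 SD. Within levels of U there is no LGI–SYNTAX association (true odds ratio 1). The event share e is 18% or 30%. All 552 patients enter the model.

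**Formulas:**

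1. Find the cut-point c with (1−p)·P(Z>c) + p·P(Z>c−d2) = e. The event risks are q0 = P(Z>c) without the factor and q1 = P(Z>c−d2) with it.
2. Log odds ratio per SD of LGI ≈ d1·[P(U|event) − P(U|no event)] / s, where s = √(1 + p(1−p)d1²), P(U|event) = p·q1/e and P(U|no event) = p(1−q1)/(1−e).
3. Standard error ≈ 1/√(N·e(1−e)).
4. With k = log odds ratio / standard error, false-positive rate = Φ(k−1.96) + Φ(−k−1.96).

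**Worked case:** p = 0.40, d1 = 0.8, d2 = 0.6, e = 0.30.

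- q0 = 0.216 and q1 = 0.426; check: 0.6×0.216 + 0.4×0.426 = 0.300.
- P(U|event) = 0.4×0.426/0.30 = 0.568; P(U|no event) = 0.4×0.574/0.70 = 0.328; difference 0.240.
- s = √(1 + 0.24×0.64) = 1.074. Log odds ratio ≈ 0.8×0.240/1.074 = 0.179, so the odds ratio is about 1.20.
- Standard error ≈ 1/√(552×0.21) = 0.093; k ≈ 1.92; false-positive rate ≈ 48–49%.

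**All cases** (logistic slope solved numerically, which differs little from the approximation above):

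| Factor | Shifts LGI/SYNTAX (SD) | e | q0 | q1 | Spurious OR per SD | False positives |
|---|---|---|---|---|---|---|
| ACS type, p = 0.40 | 0.4/0.4 | 18% | 0.137 | 0.244 | 1.071 | 9.4% |
| | 0.4/0.4 | 30% | 0.244 | 0.384 | 1.065 | 10.4% |
| | 0.6/0.5 | 18% | 0.127 | 0.260 | 1.133 | 20.4% |
| | 0.6/0.5 | 30% | 0.230 | 0.405 | 1.123 | 23.7% |
| | 0.8/0.6 | 18% | 0.116 | 0.276 | 1.215 | 41.4% |
| | 0.8/0.6 | 30% | 0.216 | 0.426 | 1.197 | 48.4% |
| Sex, p = 0.70 | 0.2/0.3 | 18% | 0.128 | 0.202 | 1.021 | 5.4% |
| | 0.2/0.3 | 30% | 0.230 | 0.330 | 1.020 | 5.5% |
| | 0.3/0.5 | 18% | 0.099 | 0.215 | 1.050 | 7.3% |
| | 0.3/0.5 | 30% | 0.187 | 0.348 | 1.049 | 8.1% |

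Direct simulation at n = 552 (4,000 repeats) of the three ACS-type settings and these two sex settings agreed to within 1.3 percentage points. The highest rate was 49.2%.

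**Second parameterisation:** a factor with 40% prevalence, 25% event risk when it is absent, and its own odds ratio of 1.5 to 3 for the outcome.

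| LGI shift | Spurious OR per SD | False positives |
|---|---|---|
| 0.2 SD | 1.02–1.06 | 5–9% |
| 0.5 SD | 1.04–1.13 | 8–29% |
| 0.8 SD | 1.09–1.22 | 14–58% |

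If the factor does not shift LGI, or does not affect SYNTAX, the odds ratio is about 1.0 and the rate about 5%.

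**The case against.** A reader might infer that the adjusted odds ratio is confounded, because ACS type, route and sex drive both LGI and SYNTAX. The documents do not support that. They contain nothing relating any of the three to either measure. The calculations depend on assumed shifts and cover no bias at all. They also ignore whatever part of the effect the four existing covariates absorb.

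It is also tempting to treat ACS type as a plain common cause. Coronary anatomy may partly determine ACS type, which may then influence LGI. ACS type would then be partly an intermediate, and forcing it into the main model could over-adjust. The title speaks of association and the logistic model of predictors, so the plan does not claim a causal effect. This objection stands, and it is why ACS type belongs in a sensitivity analysis.

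A third inference is that outpatient glucose is not comparable with emergency glucose. The plan says the tests were done at admission and describes no different sampling for outpatients. Route may matter, but non-comparability is not shown.

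Larger false-positive rates can be derived. With the same three pairs of shifts, a Pearson correlation without covariates gives r = 0.04, 0.07 and 0.10, and rates of about 14%, 35% and 68%. Those figures bear on the plan's correlation analysis. They do not measure the bias in the logistic odds ratio, for which the rates are lower.

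For sex, the estimated bias is small. The case for adding it rests mainly on an unexplained omission that costs nothing to repair.

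What the objections leave untouched is that a listed variable was dropped without a reason, and that no analysis addresses acuteness although the exposure is measured at admission.

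**Conclusion.** The point holds in limited form. Residual confounding of the LGI odds ratio by ACS type, presentation route or sex cannot be excluded. Neither its presence nor its size can be determined from the documents.

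Under the stated assumptions, a difference by ACS type could by itself produce an odds ratio per SD of about 1.06 to 1.22, with a false-positive rate of about 10% to 49% in place of 5%. The corresponding rate for sex is about 5–8%. Prevalences, shifts and event shares are all assumed, and the true effect could be nil.

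Severity: should-fix. The gap limits how a significant adjusted result may be read, but it does not invalidate the analysis.

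**What to change.** 1. Add sex to the adjusted model.
2. Beside the current model, report two further LGI estimates: one additionally adjusted for ACS type and presentation route, and one within ACS-type strata. The document is written in the past tense with 552 patients already included, so label these as added sensitivity analyses, not as pre-specified.
3. State that ACS type may be partly an intermediate, and list residual confounding as a limitation.

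**Cost.** Sex is already a listed variable and needs no new data. ACS type and route are not listed and would have to be abstracted from existing 2015–2023 records. Confidence intervals become slightly wider.

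**Parameters.** The current model has 5 (LGI plus four). Sex adds 1, ACS type 2 (assuming three categories) and route 1, giving 9. At 10 events per parameter, that needs 90 events in place of 50, or 90/552 = 16.3% in place of 50/552 = 9.1%. The plan gives no event count. At assumed shares of 10%, 20% and 30%, events per parameter are 55.2/9 = 6.1, 110.4/9 = 12.3 and 165.6/9 = 18.4, if all 552 patients enter the model. If there are fewer than about 90 events, add sex only (6 parameters, 60 events, 10.9% of 552) and handle ACS type by stratified reporting.
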